3.6 Risks and Benefits

Risks to the subject will be no greater than those of a conventional UDS test. Physicians are responsible for determining whether subjects are medically indicated and would benefit from UDS testing. There is no direct subject benefit for participating other than to gather evidence of e·Sense® urodynamic catheters' clinical use.

There is also no need for any repeat catheterization or UDS testing using an approved (non-investigational) UDS catheter. UDS test results using the investigational device will be provided back to the referring physician for test interpretation. The investigational device must first pass design verification and manufacturing process validation in accordance with ISO 13485 before it can be used in this clinical investigation. Given this, the sponsor has no reason to suspect device safety and performance will be any different as compared to the currently marketed e·Sense® UDS catheter. Therefore, the data collected using the investigational device will be used in the test interpretation for each subject enrolled, unless there is reason to believe the test should be repeated. This can happen under normal (non-investigational) circumstances if the test was inconclusive².

	e·Sense® Clinical Investigation Protocol	CLN-00021-ESNS-PH01-PR-01	Version B
---	---	---------------------------	-----------

Subjects may experience temporary discomfort upon insertion of the catheters. Test duration may be slightly longer than a standard test while assessment of the study materials is being made, and so discomfort and inconvenience associated with an extended test duration may occur.

UDS testing exposes subjects to risks of urethral instrumentation which can result in infection, urethral trauma and pain³. Other risks can include transient discomfort during or following the procedure, transient dysuria or bleeding (haematuria) following the procedure, or urinary tract infection, which occurs in approximately 2-4% of subjects⁴. Autonomic dysreflexia can also occur in those patients with spinal cord injury (SCI), and those at the level of T6 or higher are particularly prone^{5,6}. As well, accidental ureter catheterization, where the ureter orifice is accidentally catheterized, can occur. A summary of the available safety data concerning these risks is presented in the Investigator's Brochure.

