- c) foetal distress, foetal death or a congenital physical or mental impairment or birth defect.

NOTE per ISO 14155: Planned hospitalization for a pre-existing condition, or a procedure required by this protocol, without serious deterioration in health, is not considered a serious adverse event.

10.1.5 Unanticipated Serious Adverse Device Effect (ISO14155:2020):

Serious adverse device effect which by nature, incidence, severity or outcome has not been identified in the current risk assessment.

NOTE: Anticipated serious adverse device effect (ASADE) is an effect which by its nature, incidence, severity or outcome has been identified in the risk assessment.

10.1.6 Severe Complications (sponsor definition):

A severe complication is defined an adverse event (whether expected or non-expected) that has been evaluated on CRF 5 as:

- Severity graded as either Severe (3) or Life-Threatening (4) and;

	e·Sense® Clinical Investigation Protocol	CLN-00021-ESNS-PH01-PR-01	Version B
---	---	---------------------------	-----------

- Study Procedure Relationship graded as Probably Related (3) or Definitely Related (4) and;
- Action taken with respect to study device required Invasive Medical Intervention (4) and/or resulted in Hospitalization (5) and;
- The outcome for the subject resulted in recovered with Major Sequelae (3), Ongoing/Continuing Treatment (4), Condition Worsened (5) or Death (6).

Or otherwise any adverse event categorized as a Serious Adverse Event (See Section 10.1.4 for definition).

NOTE: An invasive medical intervention refers to any medical intervention or oral medication treatment lasting one week (seven days) or longer. Conversely, a non-invasive treatment refers to any medical intervention or oral medication lasting less than one week (seven days).

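### Section 10.1.6 defines an invasive intervention only by its duration, so a narrow set of severe events treated by a short procedure is left out of a secondary endpoint that tolerates no event

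*Combined protocol and SAP*

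**What the plan says.** Section 10.1.6 gives two routes into the severe-complication count.

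The first has four criteria joined by **and**, all graded on CRF 5:

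- severity: "Severity graded as either Severe (3) or Life-Threatening (4) and"
- relationship: "Study Procedure Relationship graded as Probably Related (3) or Definitely Related (4) and"
- action: "Action taken with respect to study device required Invasive Medical Intervention (4) and/or resulted in Hospitalization (5) and"
- outcome: code 3 (major sequelae), 4 (treatment continuing), 5 (worsened) or 6 (death).

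The second route is an alternative: "Or otherwise any adverse event categorized as a Serious Adverse Event". Section 10.1.4 defines these as death, or a serious deterioration in health leading to life threat, permanent impairment, hospitalisation, chronic disease, or medical or surgical intervention to prevent life threat or permanent impairment. It also has a foetal limb, which hardly applies because pregnant women are excluded.

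A note then fixes the meaning of action code 4: "An invasive medical intervention refers to any medical intervention or oral medication treatment lasting one week (seven days) or longer". Its next sentence gives the converse: "a non-invasive treatment refers to any medical intervention or oral medication lasting less than one week (seven days").

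Section 11.2.1 tests the resulting severe complication-free rate against 95%, using a one-sided 95% Clopper-Pearson lower limit.

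**The concern.** The seven-day limit cannot be read as applying to oral medication alone, because the converse sentence applies it to any medical intervention. What was done to the subject plays no part. The label and its definition therefore part company in both directions: a same-day repair is non-invasive, and a week of tablets is invasive. No other section corrects this.

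Procedure-related injury is a foreseeable kind of event here. Section 3.6 states that "UDS testing exposes subjects to risks of urethral instrumentation which can result in infection, urethral trauma and pain", and it also lists accidental catheterisation of the ureter. If such an injury is treated by a short outpatient procedure, the action criterion can fail on the note alone.

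An investigator who follows the note must code a procedure against the ordinary meaning of the word, and one who follows the ordinary meaning departs from the protocol. Coding could differ across the two to four sites. The written definition carries much of the weight: the study is single-arm and open-label (Section 5.1), the sponsor classifies adverse events (Section 10.3), and there is no data monitoring committee (Section 16.3).

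**Working it through.** **1. Which events does the note alone decide?** Take an event that is graded severe and is probably or definitely related.

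| Event | Action criterion today | Outcome criterion | Counted today? | Counted if code 4 covered procedures? |
|---|---|---|---|---|
| Short procedure, full recovery, not serious | fails | fails | no | no |
| Short procedure, hospitalised, outcome 3–6 | met by code 5 | met | yes | yes |
| Short procedure to prevent life threat or permanent impairment, with serious deterioration | not needed | not needed | yes, as a serious adverse event | yes |
| Short procedure, not hospitalised, not serious, outcome 3–5 | fails on the note | met | **no** | **yes** |
| Oral course of seven days or longer, outcome 3–5 | met by code 4 | met | yes | yes |

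Only the fourth row changes. Outcome 6 drops out of it because death is always a serious adverse event. The row is narrower still because continuing treatment that itself reaches seven days becomes code 4, and permanent sequelae or chronic disease are serious where health has seriously deteriorated.

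**2. The plan's own figure.** Inputs from Sections 11.2.1 and 11.2.2: n = 60, target 95%, assumed true rate 100%, one-sided type I error 5%, stated power 99%. With x successes out of n, the lower limit is the 5% quantile of Beta(x, n − x + 1). For x = n this is 0.05^(1/n).

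- 60/60: 0.05^(1/60) = 0.9513, above 0.95, so the test passes.
- Attained type I error: 0.95^60 = 0.0461.
- Power at a true rate of 100%: 1^60 = 1, consistent with the stated 99%.

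**3. What one event does.** The p-value for n − 1 successes is 0.95^n + n × 0.95^(n−1) × 0.05.

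| Result | Lower limit | p-value | Against 95% |
|---|---|---|---|
| 60/60 | 95.13% | 0.046 | pass |
| 59/60 | 92.34% | 0.192 | fail |
| 65/65 | 95.50% | 0.036 | pass |
| 64/65 | 92.91% | 0.158 | fail |

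The test passes only with zero events at every n from 60 to 65. Tolerating one event would need at least 93 subjects.

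**4. Illustration under an assumption.** Suppose a share s of severe complications falls in the fourth row. The documents give no value for s. At a true severe-complication rate of 5%, the chance of passing is (1 − 0.05(1 − s))^n:

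| s (assumed) | n = 60 | n = 65 |
|---|---|---|
| 0 | 4.6% | 3.6% |
| 10% | 6.3% | 5.0% |
| 25% | 10.1% | 8.3% |
| 50% | 21.9% | 19.3% |

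This models undercounting only. It ignores the events that the note brings in through long oral courses, so it is not an estimate of net bias.

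**The case against.** The strongest reply is that the gap is thin and is largely covered elsewhere. Most of that stands.

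- **Other routes catch most serious cases.** Hospitalisation meets the action criterion directly. The serious-event limb names surgical intervention with no duration limit. This stands, and it leaves only the fourth row of the table.
- **The outcome criterion would exclude many short procedures anyway.** This also stands. A reader might infer that any injury repaired on the day escapes because of the note. If the subject recovers fully, the event fails the outcome criterion whatever the note says.
- **The note also widens the endpoint.** An oral course of seven days or longer meets the action criterion, though severity, relationship and outcome must still be met. The only complication to which Section 3.6 attaches a rate is urinary tract infection, at about 2–4%, or 60 × 0.02 = 1.2 to 60 × 0.04 = 2.4 expected cases in 60 subjects. How many would be severe and treated for that long is not stated. A reader might infer that the complication-free rate is overstated; the documents do not show the net direction.
- **The contrast between 60/60 and 59/60 holds under any definition of severe complication.** It is a property of the zero-event test. It shows why one coding decision matters, not how often the note causes one.
- **The events would not be hidden.** All adverse events are recorded (Section 10.2), and their number and type are summarised in the study report (Section 10.3). Only the secondary count would miss them.

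CRF 5 itself is not in the documents, so its completion instructions may say more. Nothing in the protocol indicates that they do.

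**Conclusion.** The point holds in a narrow form. Action code 4 is defined by duration alone, and that definition leaves out severe, related, non-hospitalised, non-serious events treated by a procedure of under seven days with outcome code 3, 4 or 5. Their frequency cannot be derived from the documents and is probably small. It matters because a single such event at 60 to 65 subjects would turn a pass into a fail if it were counted.

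The conclusion rests on reading the note literally, including its converse sentence, and on CRF 5 following Section 10.1.6. It does not extend to a claim that short procedures in general escape the endpoint, or that the reported rate is biased in a known direction. Severity: low.

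**What to change.** In Section 10.1.6 and the matching CRF 5 instructions, let action code 4 be met by any surgical, instrumental or other procedural intervention regardless of duration. Keep treatment lasting seven days or longer as a separate, additional trigger. Apply the same rule to events already recorded. Nothing counted today is lost, so the change can only leave the count as it is or raise it.

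This is an endpoint coding rule. It leaves clinical management, the sample size and the test unchanged.

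The cost is more than wording. Table 2 places the first 30 subjects in June to December 2020, and this version took effect on 8/24/2021. On that timeline the definition would change partway through an open-label study. It would need an amendment with ethics committee and regulatory review as Section 15 requires, and any earlier CRF 5 entries would have to be recoded. The reported complication-free rate may also become less favourable.

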10.1.7 Serious adverse device effect (ISO14155:2020)

An adverse device effect that has resulted in any of the consequences characteristic of a serious adverse event.

10.2 Data Collection

All adverse events, device deficiencies or any other event or information for potential unanticipated safety concerns shall be recorded and reported to the sponsor on the appropriate CRF:

- ESNS-PH01-CRF-01: For initial of recording of any adverse event, device deficiency or other event/information regarding a potential unanticipated safety concern.
- ESNS-PH01-CRF-05: For reporting adverse event full details
- ESNS-PH01-CRF-06: For reporting device deficiencies full details
- ESNS-PH01-CRF-07: For recording patient follow-up details

These data shall be recorded and reported for both the primary and secondary analysis populations (see Section 11.5). Where required, EC and/or regulatory authorities shall be notified within a specified time period.

10.3 Reporting

All adverse events, device deficiencies and other events or information for potential unanticipated safety concerns will be reported as soon as possible to the sponsor for evaluation. The Sponsor is responsible for the classification of adverse events and will review the Investigator's assessment to determine seriousness and relationship to the investigational device. Laborie will carefully evaluate all serious adverse events, regardless of whether or not they are related to the investigational medical device or anticipated. Likewise, not only safety endpoint events but all serious adverse events have to be assessed with regard to patient safety and are to be compared to acceptable occurrence rates.

In the case of disagreement between the Sponsor and Investigator, the Sponsor shall communicate both opinions to the concerned parties (EC/regulatory authority, where

	e·Sense® Clinical Investigation Protocol	CLN-00021-ESNS-PH01-PR-01	Version B
---	---	---------------------------	-----------

required). Reports to EC and regulatory authorities will be made within the required time period. All Investigators shall be informed, in writing, of all the serious adverse events at all investigation sites that have been reported to the sponsor, and ensure that they are reported to their EC.

Investigators shall make reference to the Safety Reporting Guidelines (ESNS-PH01-SRG-01) for details on country-specific safety reporting requirements and other pertinent details.

Should a suspension or premature termination occur due to a serious health threat, the EC and regulatory authority shall be notified as well (see Section 5.3). Deviations from this protocol under emergency circumstances where the rights, safety or well-being of the subject were of concern, must be reported as soon as possible to the sponsor, EC and/or regulatory authority where required (see Section 14).

The number and type of adverse events will be summarized in the clinical study report.

10.4 Foreseeable Events

For a complete Risk Management Report please refer to the Risk Management File. The residual risks have been deemed acceptable and the benefits overweighs the risks. Please also refer to Section 3.6 above and the Investigator's Brochure for a detailed analysis of expected risks.

10.5 Contact Information

In the event of a serious adverse event or serious adverse device effect, please inform Laborie personnel within 24 hours. A safety reporting telephone line is available at the number below:

[contact] (North American, Eastern Time)

10.6 Follow-Up

Site personnel will telephone the subject three to five days post-test and inquire as to whether any adverse events have occurred after their UDS test.

If an adverse event occurred, any follow-up medical intervention prescribed is at the discretion of the Investigator and shall be recorded on the subjects' Adverse Event Case Report Form (ESNS-PH01-CRF-05). Please refer to Section 7.5 above for further detail.

11 STATISTICAL CONSIDERATIONS

11.1 Primary Analyses

11.1.1 Primary Endpoint

The primary safety and effectiveness endpoint is a composite endpoint based on clinician response after each UDS study using the investigational device (e·Sense® catheter) to determine whether the urodynamic use of the catheter was clinically adequate (success) or inadequate (failure). A procedure is considered a success when the clinician determines the investigational device to be both safe and effective as per the Investigator Assessment on CRF 1. If these criteria are not met, the procedure is classified as a failure. The primary effectiveness

	e·Sense® Clinical Investigation Protocol	CLN-00021-ESNS-PH01-PR-01	Version B
---	---	---------------------------	-----------

hypothesis is a comparison of the lower bound for the estimate of the success rate to a minimally acceptable target value of 75%:

H_0 : Composite Safety and Effectiveness Success Rate is $\leq 75\%$

versus

H_A : Composite Safety and Effectiveness Success Rate is $> 75\%$

This 1-sided hypothesis will be evaluated by comparing the lower limit of the 97.5% 1-sided Clopper-Pearson confidence interval to the target value. If the lower limit of the 97.5% 1-sided Clopper-Pearson confidence interval is greater than the target value, the null hypothesis will be rejected, and it will be concluded that an effectiveness rate $\leq 75\%$ is inconsistent with the investigation findings. The lower limit of the 97.5% 1-sided Clopper-Pearson confidence interval is identical to the lower limit of a 2-sided 95% Clopper-Pearson confidence interval, so the 2-sided Clopper-Pearson 95% confidence interval may be calculated for computational ease. In addition, a 1-sided, 1-sample binomial test will be performed to calculate a p-value. $P < 0.025$ will be considered statistically significant.

11.1.2 Sample Size Determination & Power:

The null hypotheses for the primary composite effectiveness endpoint is designed to rule out success rates $\leq 75\%$. Based on clinical judgement and previous testing, the true success rate for both safety and effectiveness are assumed to exceed 95%. Thus, the power calculation assumes a true success rate of 96% for the composite safety and effectiveness endpoint.

Power was determined by 10,000 binomial simulations (assuming success rate 96%) for each sample size, and power was calculated as the proportion of simulations for which the null hypothesis would be rejected based on the lower limit of the 2-sided 95% Clopper-Pearson confidence interval. Analysis of 30 subjects would provide 88% power to rule out a success rate $\leq 75\%$ when the true success rate is assumed to be 96%, based on a 1-sided test with type I error rate of 2.5%. This primary analysis and endpoint requires a minimum of 30 subjects to ensure adequate power¹⁵.

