6.4 Recruitment Plans

To satisfy the primary objective, the target enrolment is a minimum of 30 subjects with an attempted UDS study (e·Sense® catheter has made contact with the patient's body). To satisfy the secondary objective, the target enrolment is a minimum 60 subjects with an attempted UDS study (e·Sense® catheter has made contact with the patient's body). In addition, the study sponsor will allow up to 65 subjects (5 additional) during the allowable recruitment and project time given the minimum recruitment goals are met. Please refer to Section 11 for details on sample size determination.

Subjects who are visiting the UDS clinic for their medically indicated UDS test will be approached regarding participation in this study. It is estimated that study-wide recruitment of 60 subjects should take approximately 18 weeks of active recruitment at each site. Recruitment will be monitored by Laborie through scheduled meetings with the site co-ordinator. If the subject signs the informed consent, this will be treated as the point of enrolment.

The minimum number of clinical sites shall be two. The maximum number of sites allowed for this study shall be four. A minimum of 15 subjects per site is required to ensure proper distribution across sites. Once each site has met the minimum recruitment of 15 subjects, the sponsor will be informed. Following this, the site may have the option to continue recruitment until the study-wide maximum is reached, based on the discretion of the sponsor. Additional enrolment following the minimum recruitment goal will be dictated by the final number of sites initiated.

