11.7 Interim Analysis

Once 30 primary analysis population subjects complete the study the primary composite safety and effectiveness analysis will be conducted for regulatory purposes. Once all (60-65) subjects are complete, the secondary endpoint analysis will be performed. In addition, the exploratory endpoints will be assessed and an exploratory analysis of the composite (primary) safety and effectiveness endpoint including all subjects will be performed.

There are currently no criteria for stopping the study early on statistical grounds. Refer to Section 5.3 for details about suspension or premature termination.

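### The 88% power at 30 subjects is correct, but 30 is not the minimum the plan calls it; fixing the primary analysis at 33 of the 60 to 65 planned subjects would give 96%, if no ratings have been reviewed

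*Combined protocol and SAP*

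**What the plan says.** Section 11.1.1 compares the composite safety and effectiveness success rate with a "minimally acceptable target value of 75"%. The decision rule is exact: "If the lower limit of the 97.5% 1-sided Clopper-Pearson confidence interval is greater than the target value, the null hypothesis will be rejected".

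Section 11.1.2 gives the planning inputs. On the true rate, "the power calculation assumes a true success rate of 96% for the composite safety and effectiveness endpoint". On power, "Analysis of 30 subjects would provide 88% power to rule out a success rate" of 75% or less, "based on a 1-sided test with type I error rate of 2.5"%. It concludes that "This primary analysis and endpoint requires a minimum of 30 subjects to ensure adequate power".

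Section 6.4 repeats the figure as a floor: "To satisfy the primary objective, the target enrolment is a minimum of 30 subjects with an attempted UDS study". Section 11.7 fixes the timing: "Once 30 primary analysis population subjects complete the study the primary composite safety and effectiveness analysis will be conducted for regulatory purposes". The study then continues to 60 to 65 subjects for the secondary endpoint, and the primary endpoint in all subjects is analysed only as exploratory.

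The plan sets no numeric power target and does not say why 30 was preferred to neighbouring sizes.

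**The concern.** An exact binomial rule moves in steps. The number of failures allowed is a whole number. While it stays constant, each further subject is one more chance to fail, so power falls until the next failure is allowed. A size partway along such a step can have less power than a smaller size, and much less than a slightly larger one.

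Thirty is partway along a step. If smaller sizes do better and 33 does much better, then calling 30 a minimum misdescribes the test. It also suggests that a small overrun is harmless, when analysing 31 or 32 would lower power.

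At stake is an 11.7% chance of missing the only primary test when the device performs exactly as assumed. Under section 11.7 the later all-subject analysis is exploratory, so it cannot rescue a miss at 30.

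**Working it through.** **Inputs** (sections 11.1.1 and 11.1.2): null rate p0 = 0.75; planning rate p1 = 0.96; one-sided α = 0.025; reject when the Clopper-Pearson lower limit exceeds 0.75; n = 30; stated power 88%.

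**Formulas.** For each n, the critical count r is the smallest number of successes with P(X ≥ r | n, 0.75) ≤ 0.025. This is equivalent to the lower limit exceeding 0.75, where the lower limit is the 0.025 quantile of Beta(r, n − r + 1). Actual size = P(X ≥ r | n, 0.75). Power = P(X ≥ r | n, 0.96).

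**The plan's figure.** At n = 30, 28/30 has a lower limit of 0.779 and passes; 27/30 has 0.735 and fails. So r = 28, and at most two failures are allowed. With a failure probability of 0.04:

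- P(0 failures) = 0.96^30 = 0.2939
- P(1 failure) = 30 × 0.04 × 0.96^29 = 0.3673
- P(2 failures) = 435 × 0.04² × 0.96^28 = 0.2219

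The sum is 0.8831, which reproduces the stated 88%. Actual size is 0.0106.

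**Neighbouring sizes, same rule:**

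| n | Successes needed | Failures allowed | Lower limit at r | Actual size | Power at 96% |
|---|---|---|---|---|---|
| 26 | 25 | 1 | 0.804 | 0.55% | 72.1% |
| 27 | 25 | 2 | 0.757 | 2.07% | 90.8% |
| 28 | 26 | 2 | 0.765 | 1.66% | 90.0% |
| 29 | 27 | 2 | 0.772 | 1.33% | 89.2% |
| 30 | 28 | 2 | 0.779 | 1.06% | 88.3% |
| 31 | 29 | 2 | 0.786 | 0.84% | 87.4% |
| 32 | 30 | 2 | 0.792 | 0.67% | 86.5% |
| 33 | 30 | 3 | 0.757 | 2.05% | 95.8% |

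At n = 32, 29/32 has a lower limit of 0.7498 and just fails, so the third failure is first allowed at 33. There the terms for 0 to 3 failures are 0.2600 + 0.3575 + 0.2383 + 0.1026 = 0.9584.

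**Risk of missing the primary at 96%:** 1 − 0.883 = 11.7% at n = 30 and 1 − 0.958 = 4.2% at n = 33. The reduction is 7.5 percentage points, about two thirds of the risk.

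**Sensitivity to the true rate:**

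| True rate | n = 30 | n = 33 |
|---|---|---|
| 95% | 81.2% | 91.9% |
| 96% | 88.3% | 95.8% |
| 97% | 94.0% | 98.3% |
| 98% | 97.8% | 99.6% |

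The advantage of 33 holds throughout and shrinks as the true rate rises.

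**Delay.** Table 2 allots 20 weeks to the first 30 subjects, so three more take 3 × 20/30 = 2 weeks at that rate. Table 2 also dates the first 30 to June to December 2020 and the remainder to September to December 2021. If subjects 31 to 33 fall in the second period, the wait includes that gap.

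**The case against.** The strongest reply is that nothing is miscalculated. The 88% reproduces, the error rate is held, and there is no stated power target for 88% to miss. That is right, and it limits this to an efficiency point plus one inaccurate sentence.

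A reader might infer from the table that 27 is simply the better choice. It is not a safe one. Section 11.5 defines the primary population by catheterisation, not by a completed rating, and section 12.3 leaves missing values missing. One missing rating takes 27 to 26 and power to 72.1%. From 30, losing one, two or three ratings gives 89.2%, 90.0% or 90.8%, so 30 has a cushion. The same fragility applies to 33: one missing rating gives 32 and 86.5%, below the present 88.3%. This objection stands, and it is why the analysis set should count completed ratings.

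The 30-subject rule is also stricter: 28/30 (93.3%) against 30/33 (90.9%). For a single-arm study resting on a clinician's yes/no judgement, a sponsor may prefer that. But the plan states 2.5% as its error rate, and 2.05% is within it.

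Finally, the change may come too late. Version B took effect on 24 August 2021, after Table 2's date for the first 30 subjects. The documents do not say whether the analysis was run. The study is open-label, so ratings could be known without a formal analysis. A result of 27/30 fails, yet three further successes would make it 30/33, a pass; extending after seeing the ratings would not preserve the error rate.

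**Conclusion.** The point holds as a conditional, low-cost improvement. Power at a true rate of 96% is 88.3% at 30 and 95.8% at 33, with actual size rising from 1.06% to 2.05%. The minimum claim is not right on the plan's own test, because 27, 28 and 29 each have more power than 30; a drift to 31 or 32 would reduce power to 87.4% or 86.5%.

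The documents do not support a stronger reading in which the power figure is wrong, the test is invalid, or 88% is inadequate.

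The figures assume independent ratings, a common true rate and exactly n completed ratings. The gain is available only if the size is fixed before any of the first 30 ratings are reviewed, which the documents leave open.

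**What to change.** **If the primary ratings from the first 30 subjects have not been reviewed:**

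- Set the primary analysis at exactly the first 33 primary-analysis-population subjects with a completed CRF 1 safety and effectiveness rating. Report any subject passed over for want of a rating, with the reason.
- State the criterion as 30/33 or better (lower limit 75.7%) and the power as 96%.
- Replace the minimum wording with a fixed number, and align sections 6.4, 9.1, 11.1.2, 11.7 and Table 2. The study total stays at 60 to 65.

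The cost is a protocol amendment and a later primary read-out: about two weeks at Table 2's rate for the first 30, longer if the three subjects fall after the gap between December 2020 and September 2021. No extra subjects are needed. The lower required observed rate should be accepted knowingly.

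**If those ratings have been seen or analysed:** keep 30, analyse exactly the first 30, and correct only the sentence calling 30 the minimum. For example, say that 30 was chosen and gives 88% power under the stated rule. This costs one sentence.
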